### **Processing of results**

Statistical analysis, data visualization and predictive analysis will be carried out through Statgraphics software (Statgraphics Technologies, Inc., The Plains, Virginia). Features of the population included in the study will be analyzed by descriptive techniques. In

all evaluations made the results will be expressed as arithmetic mean and deviation

standard. The statistical analysis of the parametric data will be performed with the Student's T test for measurements paired and unpaired, comparing data at the start and at the end and then between the control and the intervention group. P-values  $<0.05$  will be considered statistically significant.

### **Study monitoring**

The study will be performed in accordance with the protocol and international Good Clinical guidelines Practice, and with the current regulations on clinical trials and those of reference for natural mineral waters.

### **Ethical aspects**

The current version of the Declaration of Helsinki (2013), the reference for the ethical aspects of this clinical trial will be respected by all who are engaged in this research.

The protocol, informed consent and any other material will be reviewed by the Ethics Committee.

All eligible subjects must be informed of the purpose of the study, possible risks, and benefits of the proposed interventions, and must obtain an information document stating the nature, the purpose and course of the study.

The data of the study subject will be confidential and used in accordance with current legislation on protection of sensitive data and privacy legislation.

### **Outcomes**

The intake of an easily assimilable dose of calcium from a resource such as bicarbonate water calcium and sodium levels, may be able to determine

improvements in turnover markers

bone and also joint functionality and elasticity, decreasing the risk of bone fractures.

**Study investigator:** [name], Full Professor of Food Chemistry,

Department of Pharmacy, University of Salerno, [name],  
[name]- Nutritional research laboratory Nutriketo\_Lab,  
San Giuseppe hospital Moscati, [name]

**Doctor:** [name], Scientific Director of the Research Laboratory

nutritional Nutriketo\_Lab, San Giuseppe Moscati hospital, [name], 83100Avellino Av

**Address:** Nutritional research laboratory Nutriketo\_Lab, Company

San Giuseppe Moscati hospital, [name]

**Study sponsor:** SGAM SpA

- Parathyroid hormone (PTH)

- Sodium S/U/DU/(SG)ER-
- C-terminal collagen telopeptide (CTX) (S)
- Total cholesterol
- HDL
- LDL

The MOC exam (Computerized Bone Mineralometry) will be performed on 120 patients at time 0 and

6 months.

**STATISTICAL
ANALYSIS PLAN**

Official title: Evaluation of the effects of taking bicarbonate-calcium water in premenopausal and postmenopausal women as prevention of osteoporosis

Date of Document: January 27th, 2021

Data from scientific literature were used to calculate the sample size and evaluate the power of the clinical study, and in particular: • Meunier, PJ, Jenvrin, C., Munoz, F., de la Gueronniere, V., Garnero, P., & Menz, M. (2005).

Consumption of a high calcium mineral water lowers biochemical indices of bone remodeling in postmenopausal women with low calcium intake. *Osteoporosis international*, 16(10), 1203-1209

As a reference for the statistical calculations, a biochemical parameter was considered, which represents a primary endpoint of the study, the value of CTX (C-terminal telopeptide of type I collagen), a serum marker of bone turnover.

Both of the studies cited analyzed the effects of calcium-rich bicarbonate alkaline water in samples of women: in the first case in menopausal women and in the second in women in the 18-45 age range.

The results of the two studies are reported in the summary table.

Meunier et al., 2005		
S. CTX (pmol/L)	Control group (n=43) 2	Intervention group (n=44)
baseline	0.503±0.039	0.542±0.032
month 6	0.591±0.037	0.449±0.034
Wynn et al., 2009		
S. CTX (g/L)	Control group (n=15)	Intervention group (n=15)
baseline	0.380±0.115	0.479±0.261
weeks 4	0.389±0.110	0.401±0.234

Predictive statistical analysis was determined using Statgraphics software (Statgraphics Technologies, Inc., The Plains, Virginia).

Below are the results.

The power of the test (1- β) to be obtained (95%) was considered as factors for the calculation of the sample size, i.e. the probability of rejecting the null hypothesis when there is a real difference, the minimum difference between the treatments (control and intervention group), the variability of the measure and finally the level of significance α (5%), i.e. the probability of obtaining a statistically significant difference when in fact there is no difference.

First analysis (Meunier et al., 2005)

Sample-Size Determination

Parameter to be estimated: difference between two normal means

Desired power: 95,0% for difference = 0,142 versus difference = 0,176

Type of alternative: not equal

Alpha risk: 5,0%

[figure not shown]
Sigma: 0,034 (to be estimated)

The required sample size is 28 observations from sample 1 and 28 observations from sample 2.

The StatAdvisor

This procedure determines the sample size required when comparing the means of two normal distributions. Assuming that the standard deviations of the normal distributions equal 0,034, 28 observations are required in sample 1 and 28 in sample 2 to have a 95,0% chance of rejecting the hypothesis that $\mu_1 - \mu_2 = 0,142$ when the true $\mu_1 - \mu_2 = 0,176$ (using a two-sided test).

The result estimates that 28 subjects are needed for each group to be enrolled (control and intervention group), in order to ensure a statistical power of 0.95 with an $\alpha = 0.05$, using a two-tailed t-test.

For our study we assumed to recruit 30 subjects for each group (the results of the statistical analysis suggest 28 subjects for each group). Therefore, always using these available data in terms of mean, standard deviation and difference between treatments, we evaluate the power of the study at 95% confidence.

Parameter to be estimated: difference between two normal means

Sample sizes: 30 and 30

[figure not shown]
Confidence level: 95,0%

Sigma: 0,034 (to be estimated)

The tolerance for the difference will be +- 0,0175726

The StatAdvisor

This procedure determines the sample size required when comparing the means of two normal distributions. Assuming that the standard deviations of the normal distributions equal 0,034, 30 observations in the first sample and 30 in the second sample will estimate the true $\mu_1 - \mu_2$ to within $\pm 0,0175726$ with 95,0% confidence.

Second analysis (Wynn et al., 2009)

The same procedure is repeated using the data of the second scientific article cited.

Sample-Size Determination

Parameter to be estimated: difference between two normal means

Desired power: 95,0% for difference = 0,012 versus difference = 0,246

Type of alternative: not equal

[figure not shown]
Alpha risk: 5,0%

Sigma: 0,234 (to be estimated)

The required sample size is **28** observations from sample 1 and **28** observations from sample 2.

The StatAdvisor

This procedure determines the sample size required when comparing the means of two normal distributions. Assuming that the standard deviations of the normal distributions equal 0,234, 28 observations are required in sample 1 and 28 in sample 2 to have a 95,0% chance of rejecting the hypothesis that $\mu_1 - \mu_2 = 0,012$ when the true $\mu_1 - \mu_2 = 0,246$ (using a two-sided test).

Parameter to be estimated: difference between two normal means

Sample sizes: 30 and 30

[figure not shown]
Confidence level: 95,0%

Sigma: 0,234 (to be estimated)

The tolerance for the difference will be +/- 0,120941

The StatAdvisor

This procedure determines the sample size required when comparing the means of two normal distributions. Assuming that the standard deviations of the normal distributions equal 0,234, 30 observations in the first sample and 30 in the second sample will estimate the true $\mu_1 - \mu_2$ to within +/- 0,120941 with 95,0% confidence.

Both statistical analyzes agree with our choice to recruit if possible 30 subjects (instead of 28) for each group (control and intervention group), assuming an extra quota for a probable drop-out. The power of the study considered 95% is high and this increases the necessary number of patients to be enrolled. During the first analysis (data from Meunier et al., 2005), as the power of the study increases, the number of subjects for each group increases, namely:

power 80% 17 subjects;

power 85% 19 subjects;

power 90% 23 subjects;

power 95% 28 subjects.

In the absence of a pilot study, information from the scientific literature had to be used a priori.

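### Both sample-size runs test a non-zero null set exactly one SD from the alternative, so the 28 per group and 95% power do not follow from the cited effects

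*SAP*

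**What the plan says.** The SAP sizes the trial on serum CTX, using two published studies: one in menopausal women (first source) and one in women aged 18 to 45 (second source).

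- **First analysis:** "Desired power: 95,0% for difference = 0,142 versus difference = 0,176", with "Sigma: 0,034 (to be estimated") and "Type of alternative: not equal". The result is 28 per group.
- **Second analysis:** "Desired power: 95,0% for difference = 0,012 versus difference = 0,246", with "Sigma: 0,234 (to be estimated"). The result is again 28 per group.

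The software's explanatory text confirms how the inputs were read. The sample is said "to have a 95,0% chance of rejecting the hypothesis that" the mean difference equals 0.142 (first run) or 0.012 (second run).

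For 30 per group the First analysis announces that "we evaluate the power of the study at 95% confidence"; the output that follows is a tolerance of ±0.0175726 (±0.120941 in the Second analysis). The closing paragraph concludes: "Both statistical analyzes agree with our choice to recruit if possible 30 subjects (instead of 28) for each group". It also lists 17, 19, 23 and 28 subjects per group for 80, 85, 90 and 95% power.

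The SAP's opening text defines alpha as the chance of a significant result when no difference exists. The protocol (Processing of results) plans ordinary paired and unpaired Student's t-tests and names no non-zero null. Its Sample size section gives no numbers apart from alpha.

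**The concern.** The hypotheses given to the software are not the ones the trial will test. The trial asks whether CTX differs between waters, so the null difference is zero. The calculation asks whether a difference of 0.142 (or 0.012) can be told apart from a larger one. The observed effects, which should have informed the alternative, became the null.

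The alternatives have no source of their own; each is the null plus sigma. The standardised gap is then 1 by construction, and any published data entered this way would give 28.

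This is the only numerical justification of sample size in either document, and it concerns an outcome the SAP calls a primary endpoint. A reader would take a null result as coming from a trial with 95% power for the effects seen in the literature, and could wrongly treat it as evidence of no effect.

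**Working it through.** **Inputs (SAP summary table and software output)**

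| | First source | Second source |
|---|---|---|
| Final control CTX | 0.591 ± 0.037 (n=43) | 0.389 ± 0.110 (n=15) |
| Final intervention CTX | 0.449 ± 0.034 (n=44) | 0.401 ± 0.234 (n=15) |
| Absolute difference | 0.591 − 0.449 = 0.142 | 0.401 − 0.389 = 0.012 |
| Null entered | 0.142 | 0.012 |
| Sigma entered | 0.034 | 0.234 |
| Alternative entered | 0.176 = 0.142 + 0.034 | 0.246 = 0.012 + 0.234 |

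In the second source the final mean is higher in the intervention arm, opposite to the hoped-for effect.

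**1. Reproducing the plan's figure.** Power of the two-sample t-test depends on d = (alternative − null)/sigma.

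- First: (0.176 − 0.142)/0.034 = 1
- Second: (0.246 − 0.012)/0.234 = 1

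With d = 1 and two-sided alpha 0.05, the noncentral t gives 17, 19, 23 and 27 per group for 80, 85, 90 and 95% power. The SAP has 17, 19, 23 and 28. Power at 28 per group is 0.957. The SAP's figures are thus reproduced to within one subject, and both runs are the same calculation.

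**2. The same inputs against a null of zero.**

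- First source: d = 0.142/0.034 = 4.18. Three per group give 96% power; at 30 per group power is about 100%.
- Second source: d = 0.012/0.234 = 0.051. Power at 30 per group is 5.4%, and 9,884 per group are needed for 95%.

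Neither source yields 28.

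**3. The tolerance.** The half-width of a 95% confidence interval for a difference in means is t(0.975, 58) × sigma × √(2/30), with t = 2.0017 and √(2/30) = 0.2582.

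- 2.0017 × 0.034 × 0.2582 = 0.01757
- 2.0017 × 0.234 × 0.2582 = 0.12094

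Both match the SAP. They measure precision; power at 30 per group was not computed.

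**4. What the design can detect (null of zero, two-sided alpha 0.05).**

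| Comparison | 80% power | 95% power |
|---|---|---|
| 30 v 30 (within a menopausal stratum) | 0.74 SD | 0.95 SD |
| 28 v 28 (if two per group drop out) | 0.76 SD | 0.98 SD |
| 60 v 60 (strata combined) | 0.52 SD | 0.66 SD |

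At sigma 0.234, 30 v 30 corresponds to differences of 0.172 (80%) and 0.222 (95%). These are 44% and 57% of the 0.389 control mean.

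**5. Sensitivity, on assumptions the documents do not settle.**

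- The SAP does not say whether ± is an SD or a standard error. The first source's values (0.032 to 0.039) are several times smaller than the second's (0.110 to 0.261) for the same marker, although the table's unit labels differ. If they are standard errors, the SD is 0.034 × √44 = 0.226 (intervention arm) or 0.234 (pooled with 0.037 × √43 = 0.243). Power for 0.142 at 30 per group is then 64 to 67%, and 67 to 72 per group are needed for 95%.
- Change from baseline in the second source is 0.401 − 0.479 = −0.078 (intervention) and 0.389 − 0.380 = +0.009 (control), a difference of −0.087. No SD of change is given. Power at 30 per group is 29% with SD 0.234, and 44% with the pooled week-4 SD √((0.110² + 0.234²)/2) = 0.183.

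**The case against.** The strongest reply is that t-test power depends only on the standardised gap. Against a null of zero, 28 per group does give 95.7% power for a true 1-SD difference, and the 17/19/23/28 list is right to within one subject for that target. This stands: the number is not a slip of arithmetic. But the SAP does not offer 1 SD as its target. It presents 28 as derived from the published means, SDs and differences, and neither published effect is 1 SD.

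A second reply is that 5.4% power and about 9,880 per group are not useful design figures, because 0.012 runs the wrong way and ignores the baseline imbalance in that study. This is fair. Those figures show that 28 does not follow from the second source; they are not a target. The change from baseline is more informative and still gives only 29 to 44% power.

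A third is that the first source is amply powered at face value. That holds only if ±0.034 is an SD; read as a standard error, power falls to 64 to 67%.

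Finally, the tolerance is described correctly in the software text, and only the lead-in sentence calls it power. That part is minor. It is also true that correcting the point changes no patient numbers, test or endpoint.

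**Conclusion.** The calculation is wrong as written and must be corrected. The arithmetic is sound, but the hypotheses are not those of the trial. The apparent agreement between the two analyses is an artefact of setting the gap equal to sigma.

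The 95% claim holds only for a true difference of about one SD (0.95 SD at 30 per group), which the plan neither states nor justifies. The error does not run one way: with the SAP's inputs taken literally, 30 per group is far more than the first source requires and far too few for the second. These results rest on a null of zero, two-sided alpha 0.05, equal SDs, the final-visit differences in the SAP table, and ± read as SD. The standard-error and change-from-baseline readings are sensitivity ranges, and both fall well short of 95% power at 30 per group.

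**What to change.** In the SAP:

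1. Redo both calculations with a null of zero. State whether each ± is an SD or a standard error, and whether the effect is a final value or a change from baseline.
2. Delete the statements that 28 per group ensures 95% power and that the two analyses agree. On the present inputs the corrected results (3 and about 9,880) cannot justify 30 per group.
3. Keep 120 women and state what they deliver. At 30 v 30, this is 80% power for 0.74 SD and 95% for 0.95 SD. With strata combined at 60 v 60, it is 0.52 and 0.66 SD. Add the 28 v 28 figures (0.76 and 0.98 SD) if two per group are the dropout allowance.
4. Label the 17/19/23/28 list as valid only for a true difference of 1 SD.
5. Describe the tolerance as the 95% confidence-interval half-width at 30 per group, and correct the sentence that calls it power.

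The cost is one recalculation and revised SAP wording. No participants or procedures are added. The blanket 95% claim is replaced by a less favourable statement of what the trial can detect.

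### Sigma 0.034 in the SAP's first analysis is very probably a standard error; if so, the tolerance at 30 vs 30 is about ±0.12, not ±0.0176, and 95% power is not shown for postmenopausal women

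*SAP*

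**What the plan says.** The SAP calls serum CTX a primary endpoint and bases its sample size on it. Its summary table gives, for the first study (menopausal women), 0.503±0.039 and 0.591±0.037 at baseline and month 6 in the control arm ("Control group (n=43"), and 0.542±0.032 and 0.449±0.034 in the intervention arm (n=44). The ± is not labelled.

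The First analysis takes 0.034 as the SD: "Assuming that the standard deviations of the normal distributions equal 0,034". The contrast entered is "Desired power: 95,0% for difference = 0,142 versus difference = 0,176". The result is 28 per group "in order to ensure a statistical power of 0.95", "using a two-tailed t-test". For 30 vs 30 it adds: "The tolerance for the difference will be +- 0,0175726". The SAP closes with "Both statistical analyzes agree with our choice to recruit if possible 30 subjects".

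The Protocol (Processing of results) plans paired and unpaired t-tests, "comparing data at the start and at the end and then between the control and the intervention group". It does not say whether the between-group test uses final values or changes.

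**The concern.** A sample-size calculation needs the spread between women. An SE describes the precision of a mean and is smaller than the SD by a factor of root n, here between six and seven. Entering an SE as Sigma makes the trial look nearly seven times as precise as it is.

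What is at stake is how a CTX result from 30 vs 30 postmenopausal women is read. Under the printed figures, a non-significant difference looks like strong evidence against an effect. If the SD is about 0.23, the confidence interval will be roughly as wide as the effect seen in the source study, and a null result says much less.

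**Working it through.** **1. Reproducing the SAP.** Tolerance = t(0.975, 58 df) × Sigma × √(2/30) = 2.0017 × 0.034 × 0.2582 = 0.01757, which matches the printed value. For the sample size, the shift is 0.176 − 0.142 = 0.034, exactly one Sigma. The exact t calculation gives 17, 19 and 23 per group for 80, 85 and 90% power, as printed, and 27 for 95% (the SAP has 28, where power is 95.7%). A one-Sigma shift returns these numbers whatever Sigma is. The second analysis does the same (0.246 − 0.012 = 0.234 = its Sigma) and also returns 28.

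**2. SD or SE? Evidence from the summary table.**

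| Check | ± read as SD | ± read as SE |
|---|---|---|
| Baseline difference, first study (0.542 − 0.503 = 0.039) | t = 5.10, p = 2×10⁻⁶ | t = 0.039/√(0.039²+0.032²) = 0.77, p = 0.44 |
| Coefficients of variation, first study | 6-8% | 39-51% |

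The second study's coefficients of variation, with its ± read as SD, are 28-58% (for example 0.110/0.389 and 0.234/0.401). These ratios carry no units, so the differing unit labels (pmol/L and g/L) do not affect them.

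**3. Conversion if SE (SD = SE × √n).**
- Month 6: control 0.037 × √43 = 0.243; intervention 0.034 × √44 = 0.226; pooled 0.234.
- Baseline: control 0.039 × √43 = 0.256; intervention 0.032 × √44 = 0.212.

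**4. Tolerance at 30 vs 30.** 2.0017 × SD × 0.2582 gives ±0.117 (SD 0.226), ±0.121 (0.234) and ±0.125 (0.243). The pooled value is 0.121/0.0176 = 6.9 times the printed one. As a cross-check, the first study's own month-6 SE of the difference would be √(0.037²+0.034²) = 0.0502. Its 95% half-width with 43 and 44 women would then be ±0.100, and a smaller trial cannot reach ±0.0176 with the same comparison.

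**5. Power against zero, postmenopausal, final values.** Effect 0.591 − 0.449 = 0.142; two-sided t-test, alpha 0.05, noncentral t.

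| SD | 30 per group | 28 per group | 60 per group |
|---|---|---|---|
| 0.226 | 67% | 64% | 93% |
| 0.234 | 64% | 61% | 91% |
| 0.243 | 61% | 58% | 89% |

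At 30 per group, 95% needs an SD of at most 0.150. All four converted SDs (0.212-0.256) exceed that.

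**6. Power against zero, postmenopausal, change.** Effect (0.542 − 0.449) + (0.591 − 0.503) = 0.093 + 0.088 = 0.181. In each arm, SD² of change = SD₀² + SD₆² − 2r·SD₀·SD₆, then averaged over arms. The correlation r is an assumption, since the documents give none.

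| r | SD of change | Power, 30 vs 30 |
|---|---|---|
| 0.3 | 0.278 | 70% |
| 0.4 | 0.257 | 76% |
| 0.5 | 0.235 | 84% |
| 0.6 | 0.210 | 91% |
| 0.7 | 0.182 | 97% |

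95% is reached at r of about 0.67.

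**7. Premenopausal, second study.** The difference in change is (0.479 − 0.401) + (0.389 − 0.380) = 0.078 + 0.009 = 0.087. By the formula in step 6, power at 30 vs 30 is about 31% at r = 0.3, 40% at 0.5, 60% at 0.7 and 77% at 0.8. The final-value difference is only 0.401 − 0.389 = 0.012, with the intervention arm higher.

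**The case against.** The strongest reply is that the SE reading is an inference. The ± is unlabelled and the cited paper is not part of the documents. The baseline check assumes comparable arms, and the coefficient check compares menopausal women with women aged 18-45. That stands: the tolerance and power figures are conditional, and the first step has to be to look in the paper. Even so, both checks point the same way and by a wide margin.

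A second reply is that Sigma did not produce the 28 or the 95%. This is also right. A reader might infer that the SE error overturns the sample size, but the one-Sigma contrast fixes it for any Sigma. Taken alone, the Sigma error damages only the tolerance. If only the contrast were corrected and 0.034 kept, power for 0.142 would come out at essentially 100%. A usable figure needs both corrections.

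A third reply is that 61-67% rests on a final-value test that the Protocol does not specify. This stands too. A between-group test on change fits the Protocol's wording equally well and does better at every correlation in the step 6 table.

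**Conclusion.** The point holds as a conditional. Sigma 0.034 is very probably an SE. If so, the SD is about 0.23 (0.226-0.243) and the tolerance at 30 vs 30 is about ±0.12 (0.117-0.125). Once the contrast is also set against zero, the claimed 95% is not shown for postmenopausal women: it is not reached on final values, and on change only if the correlation is about 0.67 or higher.

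Two stronger readings are not supported. One is that power simply is 61-67%, which ignores the change analysis that the Protocol leaves open. The other is that power in premenopausal women is 38-44%. A reader gets that range by dividing the second study's difference in change (0.087) by its single-time-point SDs (0.183-0.202), which is valid only if the correlation is near 0.5.

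The results assume that the source effects carry over to this trial and that each stratum is compared as 30 vs 30.

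**What to change.** Change the SAP text only; keep the 120 women.

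1. Check in the cited paper whether ± is an SE or an SD. Label it, and the CTX units, in the summary table.
2. If it is an SE, replace Sigma 0.034 with about 0.23, state the conversion, and restate the tolerance as about ±0.12. If it is an SD, say so; Sigma and the tolerance then stand, and only the contrast needs correcting.
3. Name the between-group analysis (final value or change), compute power against a difference of zero, and replace the 95% with the figure for that analysis. Mark any correlation as an assumption. Quote 89-93% for 60 vs 60 (final values) only if a pooled analysis is planned and the same effect and SD are assumed in both strata.
4. For premenopausal women, if power is given from the 0.087, show it across the assumed correlation and report the 0.012 final-value difference beside it.

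The cost is one look at a paper and a rewrite of the sample-size text, with no change to recruitment. The drawback is that the stated power and precision become less favourable.

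### The SAP's second sample-size run does not support 95% power at 30 per arm: its 28 comes from a null-plus-one-sigma construction, and its source gives about 29–44% on the one favourable contrast

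*SAP*

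**What the plan says.** The SAP plans on serum CTX, which it calls a primary endpoint, and draws on two published studies: one in menopausal women, one in women aged 18–45. Its summary table gives these values, control first and intervention second:

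- First study, month 6: "0.591±0.037 0.449±0.034".
- Second study, baseline: "0.380±0.115 0.479±0.261".
- Second study, week 4: "0.389±0.110 0.401±0.234" (15 women per arm).

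The first analysis is specified as "Desired power: 95,0% for difference = 0,142 versus difference = 0,176", with sigma 0.034. The second is said to repeat the same procedure: "Desired power: 95,0% for difference = 0,012 versus difference = 0,246", with "Sigma: 0,234 (to be estimated"), two-sided, alpha 5%. The software output states the meaning of the two differences, namely a 95% "chance of rejecting the hypothesis that $\mu_1 - \mu_2 = 0,012$ when the true $\mu_1 - \mu_2 = 0,246". Each run returns 28 per group. The SAP concludes: "Both statistical analyzes agree with our choice to recruit if possible 30 subjects (instead of 28) for each group", the extra two being an allowance for drop-out.

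The protocol (Methods) randomises 30 premenopausal women to each of A1 and A2 and 30 postmenopausal women to each of B1 and B2. Its Processing of results section plans paired and unpaired t tests, with no baseline adjustment.

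**The concern.** The first run takes control minus intervention: 0.591 − 0.449 = +0.142, lower CTX on the test water. The same subtraction in the second study gives 0.389 − 0.401 = −0.012, slightly higher CTX on the test water. The SAP enters +0.012 without comment. It also uses an end-value difference although the two arms started 0.099 apart, and does not use the changes that its own table allows a reader to compute.

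The more basic difficulty is what 0.012 does in the calculation. It is the value to be rejected, not the effect to be detected, and the alternative lies exactly one sigma above it. The 28 per group therefore says nothing about whether 30 per arm could detect the effect seen in the source.

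The second study is the only planning source plausibly relevant to premenopausal women. If its 95% is taken at face value, a non-significant A1 versus A2 comparison could be read as good evidence that the water does nothing.

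**Working it through.** **Inputs.** From the SAP table: week-4 means 0.389 (SD 0.110) and 0.401 (SD 0.234); baseline means 0.380 (SD 0.115) and 0.479 (SD 0.261). I take the ± values as SDs, as the SAP does when it uses 0.234 as sigma. From the second run: null 0.012, alternative 0.246, sigma 0.234, two-sided alpha 0.05, power 0.95. Planned size: 30 per arm.

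**1. Reproduce the stated 28.** Shift = 0.246 − 0.012 = 0.234, so shift/sigma = 0.234/0.234 = 1.0.
- Normal approximation: n = 2 × (1.960 + 1.645)² / 1.0² = 26 per arm.
- Noncentral t: 27 per arm (power 0.950 at 27, 0.957 at 28).
- Tolerance at 30 per arm: t(0.975; 58 df) × 0.234 × √(2/30) = 0.12094, matching the stated 0,120941.

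The SAP's figure is reproduced to within one or two patients.

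**2. Why the two runs agree.** First run: 0.176 − 0.142 = 0.034 = sigma. Second run: 0.246 − 0.012 = 0.234 = sigma. Both have a standardised shift of 1.0, so both must return the same n whatever the sources observed.

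**3. Effect of the sign.** In a two-sided test n depends only on |shift|/sigma.
- Null −0.012, alternative one sigma away (0.222 or −0.246): 27 per arm by noncentral t, unchanged.
- Null −0.012, alternative kept at 0.246 (shift 0.258): 23 per arm, fewer.

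Correcting the sign does not raise the requirement.

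**4. What the source gives against a null of zero.** Power is from the noncentral t with 58 df and noncentrality (difference/SD) × √(30/2).

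The changes are 0.389 − 0.380 = +0.009 (control) and 0.401 − 0.479 = −0.078 (intervention), a difference of 0.087 in favour of the test water. The pooled week-4 SD is √((0.110² + 0.234²)/2) = 0.183.

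| Contrast | SD | Difference/SD | Power, 30 per arm | Per arm for 95% |
|---|---|---|---|---|
| End value, 0.012 | 0.234 | 0.051 | 5% | about 9,900 |
| Change, 0.087 | 0.234 | 0.372 | 29% | 189 |
| Change, 0.087 | 0.183 | 0.476 | 44% | 116 |

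The last two rows apply end-value SDs to a difference in change. With equal SDs at both visits the SD of change is SD × √(2(1 − r)), which equals the end-value SD when the baseline-to-end correlation r is 0.5. The documents give neither r nor an SD of change.

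**5. Sensitivity to baseline adjustment.** With residual SD = SD × √(1 − r²) and the effect held at 0.087, power at 30 per arm (SD 0.234 to SD 0.183) is:

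| Assumed r | 0.5 | 0.7 | 0.8 | 0.9 |
|---|---|---|---|---|
| Power | 37–55% | 51–72% | 66–86% | 90–99% |

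These figures are optimistic for this source. Adjusting the same table for its baseline gap gives an effect of 0.099 × slope − 0.012, where slope = r × (end SD/baseline SD). The SD ratio is 0.234/0.261 = 0.897 or 0.110/0.115 = 0.957. At r = 0.5 the effect is 0.032–0.035, and at r = 0.7 it is 0.050–0.054, both well below 0.087.

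**The case against.** The tempting stronger reading is that the reversed sign invalidates the sample size, or that the 95% power rests on an effect in the wrong direction. The documents do not support either. The 0.012 is the null, the test is two-sided, and correcting the sign leaves n at 27 or lowers it to 23. The SAP never says which arm is sample 1. On control minus intervention, +0.246 is the side where the water lowers CTX; on intervention minus control, +0.012 already has the right sign. Nor is the source adverse overall, since CTX fell by 0.078 on the test water and rose by 0.009 in controls.

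Three further objections have force:

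- **The 0.087 is a choice.** It comes from 15 women per arm with unequal baselines, may partly reflect regression to the mean, and is paired here with end-value SDs. It can only be illustrative.
- **Adjustment widens the range.** Depending on the assumed correlation, adjusted power at 0.087 runs from 37% to 99%. But adjustment is not in the planned analysis, and the high figures need both a strong correlation and an effect that the same table, once adjusted, does not give.
- **The link to premenopausal women is an inference.** The SAP speaks only of control and intervention groups and does not assign the second study to stratum A. Nor does it say that a null result will be read as no effect. It also discloses that literature was used for want of a pilot.

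None of these restores the claim that the second analysis supports 95% power at 30 per arm.

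**Conclusion.** The point holds in this form: the second run does not support 95% power with 30 per arm, and its agreement with the first is a product of the method. The cause is the use of the observed difference as the null with an alternative one sigma beyond it. The sign is a secondary inconsistency with no effect on n.

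Measured against zero, the source implies about 5% power on its end-value difference and about 29–44% on its difference in change, against the stated 95%. The latter range assumes an unadjusted two-sided comparison at 5%, 30 completers per arm, a true difference of 0.087, and an SD of 0.183–0.234 taken from end values. A higher baseline-to-end correlation would raise the power of a change or adjusted analysis; a smaller baseline-adjusted effect or drop-out would lower it.

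Relevance to A1 versus A2 is plausible but imperfect: the source covers ages 18–45 over 4 weeks, whereas the protocol enrols premenopausal women over 40 for 6 months.

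**What to change.** In the SAP, under the second analysis and its closing paragraph:

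1. Replace the 0,012/0,246 run with a test against zero. Use the difference in change, 0.087 in the beneficial direction, labelled as an illustrative effect from a study of 15 per arm with unequal baselines.
2. State the power at 30 per arm as about 29–44% for an unadjusted comparison, naming the end-value SDs assumed (0.234 and 0.183).
3. Show power for a change-score or baseline-adjusted analysis only as a sensitivity range under a stated correlation, noting that 0.087 may overstate the baseline-adjusted effect.
4. Remove the statement that both analyses agree, as far as it claims support from the second source.
5. State that a non-significant A1 versus A2 result is not evidence of no effect.

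This changes SAP wording only. Enrolment stays the same; the cost is a less favourable stated power.
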